3.3. Strata and Covariates

Subjects will be randomly assigned to treatment groups via the interactive web response system (IWRS) in a 1:1 ratio using a stratified randomization schedule. Stratification will be based on the following parameters:

- Presence or absence of lymphopenia, defined as a lymphocyte count < 200 cells/ μ L versus \geq 200 cells/ μ L of blood
- Treatment of RSV infection (yes or no) with ribavirin (oral, intravenous, or aerosolized)

For subjects with discrepancies between the stratification factor values at randomization (ie, according to IWRS) and the actual values as documented in the eCRF, the actual strata information will be used in the analyses.

In the situation that there is insufficient data in a stratum, that stratum will be pooled with the adjacent stratum, and no subgroup analysis will be conducted. For example, if there are < 4 subjects with lymphopenia, then these 4 subjects will be combined with the subjects without lymphopenia, and no subgroup analysis will be performed for the stratification factor of “presence or absence of lymphopenia”.

Efficacy endpoints will be evaluated using stratification factors as covariates in the analysis models (eg, analysis of covariance [ANCOVA]). If there are not enough subjects within a strata (< 4 subjects in 1 of the strata), the stratification factor will not be included in the analysis models.

For continuous efficacy endpoints, the baseline value of the efficacy variable will be included as a covariate in the analysis model.

3.4. Examination of Subject Subsets

Co-primary and secondary efficacy endpoints will be examined in the following subgroups if there is sufficient sample size in the subgroup:

- Stratification factors:
 - Presence or absence of lymphopenia, defined as a lymphocyte count < 200 cells/ μ L versus \geq 200 cells/ μ L of blood
 - Treatment of RSV infection (yes or no) with ribavirin (oral, intravenous, or aerosolized)
- Sex (male or female)
- Age group (< 65 or \geq 65 years)
- Race (white or all other races)

Subgroup analyses for other baseline variables such as type of transplant (autologous vs. allogeneic HCT) may be conducted.

Specified safety analyses will be examined in the following subgroups:

- Sex (male or female)
- Age group (< 65 or \geq 65 years)
- Race (white or all other races)

[figure not shown]
3.5. Multiple Comparisons

This study has 2 co-primary endpoints: the time-weighted average change in RSV log₁₀ viral load from Day 1 to Day 9, and the proportion of subjects who develop a LRTC through Day 28. To control the Type 1 error rate of 0.05 across the co-primary and secondary endpoints, a fallback approach will be applied {Wiens 2005} {Dmitrienko 2008} (see Figure 3-1).

The time-weighted average change in RSV log₁₀ viral load from Day 1 to Day 9 will be tested first at significance level of 0.01. If this null hypothesis (H₀₁) of no difference between the treatment groups is rejected then the proportion of subjects who develop an LRTC (H₀₂) will be tested with significance level of 0.05. Otherwise, the null hypothesis of no difference between treatment groups in the proportion of subjects who develop an LRTC will be tested at significance level of 0.04.

If both of the co-primary null hypotheses (H₀₁ and H₀₂) are rejected then the secondary endpoint will be tested at a significance level of 0.05. If only the null hypothesis of no difference between treatment groups in the proportion of subjects who develop an LRTC (H₀₂) is rejected, the secondary endpoint will be tested at a significance level of 0.04. If the hypothesis H₀₂ is not rejected then the secondary endpoint will not be tested.

Figure 3-1. Testing of Co-primary and Secondary Endpoints

- a Co-primary endpoint: Time-weighted average change in log₁₀ viral load
- b Co-primary endpoint: Proportion of subjects who developed LRTC
- c Secondary endpoint: Proportion of subjects who either developed respiratory failure (of any cause) requiring mechanical ventilation (invasive or non-invasive) or died prior to or on Day 28

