1.3. Sample Size and Power

Sample size and power are estimated for the co-primary endpoints with the overall alpha level 0.05 (with alpha = 0.04 allocated to the development of a LRTC and alpha = 0.01 allocated to the time-weighted average change in viral load). The sample size calculations are based on the results observed in a study that evaluated the efficacy of oral and aerosolized ribavirin treatment for preventing progression from upper to lower respiratory tract infection in HCT recipients with RSV infections (unpublished data from [name]) and published data on currently used antiviral agents for RSV infections. {Shah 2013}

Assuming the time-weighted average change in RSV log₁₀ viral load from Day 1 to Day 9 in the placebo group will be -1 log₁₀ copies/mL, with a standard deviation (SD) of 2, 100 subjects per treatment group will provide over 80% power to detect at least 1 log₁₀ decrease in presatovir group using a 2-sided significance level of 0.01.

Assuming that 30% of subjects in placebo arm will develop a LRTC, 100 subjects per treatment group will provide over 90% power to detect at least 20% reduction in the proportion of LRTC in presatovir group with a 2-sided significance level of 0.04.

Using the fallback approach and the above assumptions for the co-primary endpoints, 100 subjects per arm will provide > 95% power to declare statistical significance in either change in viral load or proportion of subjects with LRTC.

Based on an administrative review of the data occurring in mid-September 2017, Gilead decided to halt the study on 20September2017 at an enrollment of 189 subjects despite the study not achieving complete enrollment of 200 subjects. The decision was made because enrollment of the remaining 11 subjects would have had minimal impact on study outcomes.

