2.2. Efficacy Interim Analysis

Three efficacy interim analyses are currently planned for administrative purposes by the internal Gilead staff. These analyses will be performed when approximately 25%, 50% and 75% of the planned 200 subjects are enrolled and complete Day 28 of the study, respectively. A Haybittle-Peto boundary will be used for the alpha spending with an overall alpha of 0.00001 for each interim analysis and overall alpha of 0.05 for the final analysis.

This study will not be stopped early for efficacy based on the interim efficacy analysis results. The purpose of these analyses is to obtain an early assessment of the effect of presatovir. The interim efficacy results will aid internal decision-making on the further development of the presatovir program. If the results are sufficiently positive or informative, the data may be used to plan other Phase 2 and 3 studies, to seek guidance from FDA on the program development in the different subject populations, including the partial clinical hold for the pediatric program.

A Gilead Executive Team including the Vice President (VP) of Clinical Research and the VP of Biometrics will review the unblinded interim efficacy analysis results. Based on this information, the GSI Executive Team will make a decision on whether the results are informative to use in the planning of other Phase 2 and 3 studies, whether to include the results in the response to the FDA on the partial clinical hold for the pediatric program. A GSI unblinded team that is independent of the GS-US-218-0108 Study Team may be formed to support the decisions of the GSI executive team, if needed. This unblinded team will include representatives from Gilead Clinical Research, Biometrics, Regulatory Affairs, and Medical Writing groups who are not directly associated with Study GS-US-218-0108.

The GS-US-218-0108 Study Team will remain blinded to treatment assignments throughout the trial until all subjects have completed the planned study visits and the database has been locked and unblinded.

As of the finalization of this SAP, 2 efficacy interim analyses have been performed in May 2016 and September 2017 after 25% and 75% of the subjects enrolled. An alpha level of 0.00001 was used at each interim analysis using the Haybittle-Peto boundary, and the final analysis will be performed at a 0.05 level of significance.

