6.2.1. Time-Weighted Average Change in Nasal RSV Viral Load

The treatment difference in the time-weighted average change from Baseline (Day 1) to Day 9 in nasal RSV viral load (\log_{10} copies/mL) will be analyzed using a parametric ANCOVA with the baseline viral load (\log_{10} copies/mL) and stratification factors as covariates in the model. The test will be 2-sided with the significance level of 0.01. Nonparametric methods such as rank-based ANCOVA models or Wilcoxon rank sum tests may be implemented for exploratory purposes.

Adjusted means for each treatment group, 99% confidence interval (CI), and descriptive statistics (sample size, mean, SD, median, Q1, Q3, minimum, and maximum) will be presented in the descriptive summaries. Missing viral load data will be handled using the method described in Section 3.6.

6.2.2. Proportion of Subjects Who Develop a LRTC through Day 28

The proportion of subjects who develop a LRTC through Day 28 will be analyzed using a 2-sided Cochran-Mantel-Haenszel test stratified by the randomization stratification factors. The significance level used for the analysis (eg, 0.04 or 0.05) will be determined based upon the decision to reject the null hypothesis of the other co-primary endpoint as described in Section 3.5. The 2-sided 95% CI for the odds ratios between the 2 treatment groups will be constructed based on stratum-adjusted Mantel-Haenszel proportions.

The numbers and percentages of subjects who develop a LRTC through Day 28 will be provided with 95% CIs for the percentages based on the Clopper-Pearson method {Clopper 1934}.

The final analysis will be performed when all randomized subjects either complete Day 28 assessments or discontinue study prematurely.

The analyses of the co-primary endpoints will be repeated using the PP analysis set.

The primary efficacy analyses will also be repeated for the subgroups specified in Section 3.4, including the stratification factors (presence or absence of lymphopenia, treatment of RSV infection with ribavirin [yes or no] prior to randomization, sex, race, age group [< 65 or ≥ 65], type of transplant [autologous HCT or allogeneic HCT]. Adjusted mean and 95% CI will be presented by treatment group for exploratory purposes.

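### The one-directional fallback controls type I error but leaves 0.04 unused when LRTC and the secondary endpoint are both rejected; viral load could then be retested at 0.05 without raising family-wise error above 0.05

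*SAP*

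**What the plan says.** SAP 3.5 sets out the sequence, and Protocol 8.5 gives the same rule.

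- **H01, time-weighted average change in viral load (DAVG):** it "will be tested first at significance level of 0.01". SAP 6.2.1 repeats this ("The test will be 2-sided with the significance level of 0.01") and plans a 99% confidence interval.
- **H02, LRTC through Day 28:** if H01 is rejected, H02 "will be tested with significance level of 0.05. Otherwise, the null hypothesis of no difference" is tested at 0.04.
- **Secondary, ventilation or death through Day 28 (H03 below):** 0.05 if both co-primaries are rejected. If only H02 "is rejected, the secondary endpoint will be tested at a significance level of 0.04". If H02 "is not rejected then the secondary endpoint will not be tested".

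The initial split is in SAP 1.3: "with alpha = 0.04 allocated to the development of a LRTC and alpha = 0.01 allocated to the time-weighted average change in viral load". The secondary starts with no alpha of its own. SAP 2.2 keeps an "overall alpha of 0.05 for the final analysis".

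No text in either document returns alpha to H01. SAP 3.5 also cites Figure 3-1, of which only the footnotes can be read here, so whether the drawing shows a return path could not be checked.

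**The concern.** In one branch the plan holds alpha that it has no use for. Suppose DAVG gives p = 0.03 and both LRTC and ventilation-or-death are rejected at 0.04. No hypothesis is left to receive the 0.04 that H02 and the secondary have carried, yet DAVG must be reported as a failed co-primary. A procedure with the same overall error limit, and the same decisions on the other two endpoints, would have rejected it.

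DAVG is also the co-primary with the lower stated power (over 80%, against over 90% for LRTC).

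**Working it through.** **1. The plan's own power figures.** Inputs from SAP 1.3: DAVG difference 1 log10, SD 2, 100 per arm; LRTC 30% on placebo with a 20-point reduction.

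- DAVG: power = Φ(1/(2·√(2/100)) − z). The first term is 3.536. At 2-sided 0.01, z = 2.576 and power is 0.831 (0.824 by noncentral t). This reproduces the figure of over 80%.
- DAVG at 2-sided 0.05: z = 1.960, power 0.942.
- LRTC, 30% against 10% at 0.04: power 0.937 (0.911 with continuity correction). This reproduces the figure of over 90%.
- At least one co-primary, independent tests: 1 − (1 − 0.831)(1 − 0.937) = 0.989. At correlation 0.6 it is 0.962. Both agree with the stated figure of more than 95%.

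**2. Closed test.** Use these local tests:

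| Hypothesis | Reject if |
|---|---|
| H01∩H02∩H03 | p1 ≤ 0.01 or p2 ≤ 0.04 |
| H01∩H02 | p1 ≤ 0.01 or p2 ≤ 0.04 |
| H01∩H03 | p1 ≤ 0.01 or p3 ≤ 0.04 |
| H02∩H03 | p2 ≤ 0.05 |
| each single hypothesis | p ≤ 0.05 |

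Each has level at most 0.01 + 0.04 = 0.05 by Bonferroni, whatever the correlation, so the closed procedure controls family-wise error at 0.05. A hypothesis is rejected when it and every intersection containing it are rejected:

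- H02: p1 ≤ 0.01 and p2 ≤ 0.05, or p2 ≤ 0.04. Identical to the plan.
- H03: p1 ≤ 0.01, p2 ≤ 0.05 and p3 ≤ 0.05; or p2 ≤ 0.04 and p3 ≤ 0.04. Identical to the plan.
- H01: p1 ≤ 0.01; **or p1 ≤ 0.05 with p2 ≤ 0.04 and p3 ≤ 0.04**. The second part is missing from the plan.

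**3. Family-wise error by simulation** (600,000 replicates, all seven null configurations, correlation 0 and 0.5). Plan and loop-back agree at 0.047 to 0.050 in six configurations. Only the case where H01 alone is true differs: 0.010 under the plan and 0.050 with the loop-back. Simulation standard error is √(0.05 × 0.95/600,000) ≈ 0.0003.

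**4. Size of the gain at 100 per arm.** The retest helps only if 0.01 < p1 ≤ 0.05, which has probability 0.942 − 0.831 = 0.111. That is the absolute ceiling. With independent tests the gain is 0.111 × 0.937 × (secondary power at 0.04). The documents give neither secondary power nor correlations, so both are assumed. Gains in percentage points, by simulation:

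| Secondary power | corr. 0 | corr. 0.3 | corr. 0.6 |
|---|---|---|---|
| 4% (no effect) | 0.4 | 0.4 | 0.3 |
| 10% | 1.0 | 0.5 | 0.1 |
| 20% | 2.1 | 1.1 | 0.3 |
| 50% | 5.2 | 3.6 | 1.9 |
| 70% | 7.3 | 5.8 | 4.1 |

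Power for at least one co-primary does not change, because the retest needs H02 to be rejected already.

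**5. Actual enrolment.** SAP 1.3 gives 189 subjects, about 94.5 per arm. DAVG power is then 0.805 at 0.01 (0.797 by noncentral t) and 0.930 at 0.05. The FAS requires a quantifiable baseline viral load, so the analysed number may be smaller. At 85 per arm, which is purely an assumption, the figures are 0.753 and 0.903.

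**The case against.** The case for leaving the plan alone is substantial.

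- **Nothing is wrong as written.** SAP and protocol agree, type I error is controlled, and the power claimed for DAVG at 0.01 is delivered at 100 per arm. This stands.
- **The alpha is not wasted in general.** A reader might infer that DAVG is held to 0.01 for no return. The documents do not support that: the other 0.04 funds LRTC and then the secondary, and is idle only once both have been rejected.
- **The gain may be small.** A reader might take the 11% chance of a DAVG p-value between 0.01 and 0.05 as the gain. It is only a ceiling, since LRTC and the secondary must both succeed as well. As a rough guide, applying the 6.5 to 26.7% mortality after LRTI in Protocol 1.1 to LRTC rates of 30% and 10% gives deaths of about 2.0% against 0.7%, up to 8.0% against 2.7%. Secondary power at 0.04 is then about 11 to 35%, and the gain under independence is 0.104 × 0.11 to 0.104 × 0.35, about 1 to 4 points (0.104 = 0.111 × 0.937). This ignores ventilation and deaths without LRTI. The point stands.
- **Timing.** SAP 2.2 records efficacy interims in May 2016 and September 2017, with unblinded interim results reviewed by a sponsor executive team. The SAP revision log is dated 10 October 2017. Easing a threshold at that stage, even in one branch, can look informed by results. This does not defeat the change, because SAP 2.2 keeps the study team blinded until database lock, but it is a real cost.
- **The figure.** Figure 3-1 could not be inspected. The text makes a return path unlikely but does not exclude one in the drawing.

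**Conclusion.** The point holds as an improvement and not as an error. The fallback is valid but not exhaustive: in the branch where H01 is missed at 0.01 and H02 and the secondary are both rejected at 0.04, H01 may be retested at 0.05. The validity of the retest rests on a Bonferroni closed test and needs no assumption about correlation. The amended procedure is never less powerful for any of the three hypotheses, and is more powerful for H01.

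The benefit ranges from negligible to moderate and rests on a secondary power that the documents never state. DAVG power of 83% at 100 per arm rises by about 0.1 to 5 points for secondary power of 4 to 50% and correlation 0 to 0.6, and by up to about 7 points at 70%. At the 189 enrolled the starting point is about 81%. The documents do not support testing DAVG at 0.05 outright: that would exceed 0.05 overall unless alpha were taken from LRTC.

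**What to change.** Add to SAP 3.5: *If H01 is not rejected at 0.01 but H02 and the secondary hypothesis are both rejected at 0.04, H01 is retested at 0.05.* Then:

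- add the return path to Figure 3-1 if it is not already drawn;
- align SAP 6.2.1, and report a 95% confidence interval for DAVG in that branch beside the 99% interval;
- amend Protocol 8.5 and 8.5.1 to match, or declare the change in SAP 6.5 as a departure from the protocol.

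There is no cost in sample size, in overall error beyond 0.05, or in the tests of H02 and the secondary. The cost is procedural. The change must be made by the blinded study team before unblinding, with a dated record that those making it had no access to the interim efficacy results. If that cannot be shown, the existing rule should stay.

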3.6. Missing Data and Outliers

3.6.1. Missing Data

A missing data point for a given study visit may be due to any of the following reasons:

- A visit occurred in the window but data were not collected or were unusable
- A visit did not occur in the window
- A subject permanently discontinued from the study before reaching the window

Missing data can have an impact upon the interpretation of the trial data. As this study is of short duration, it is anticipated that missing data will be minimal. In general, values for missing data will not be imputed.

For laboratory data, a missing baseline value will be replaced with a screening value, if available; otherwise, it will be treated as normal (ie, Grade 0; no toxicity grade) for the summary of graded laboratory abnormalities. A retest value may be used if the first test is invalidated (eg, specimen hemolyzed).

Values will not be imputed for missing vital signs and other safety data. However, a missing baseline value will be replaced with the closest measurement prior to baseline, if available.

Missing viral load data due to premature discontinuation of the study will not be imputed as all available data will be included in the time-weighted average calculations. Intermediate missing viral load data will be imputed using the trapezoidal rule for the time-weighted average calculations, although only viral load data through Day 9 will be included in the primary endpoint calculations. As a sensitivity analysis, mixed-effects model with repeated measures (MMRM) for the absolute values and change from baseline in viral load will be applied. Similar analyses will be performed on FLU-PRO score and O₂ saturation.

All available data for subjects who do not complete the study will be included in the data listings.

3.6.2. Outliers

Outliers will be identified during the data management and data analysis process. All data, including outliers, will be included in analyses, unless otherwise specified.

3.7. Data Handling Conventions and Transformations

By-subject listings will be presented for all subjects in the All Randomized Analysis Set and sorted by subject identification (ID) number, visit date, and time (if applicable). Data collected on log forms, such as adverse events (AEs), will be presented in chronological order within subject. The treatment group to which subjects were randomized (or initially assigned) will be used in the listings.

In general, age (in years) on the date of the first dose of study drug will be used for analyses and presentation in listings. If an enrolled subject was not dosed with study drug at all, the date when baseline assessment was conducted will be used instead of the first dosing date of study drug. For screen failures, the date when the informed consent was signed will be used for age calculation. If only birth year is collected on the CRF, “01 January” will be used for the unknown birth day and month for the purpose of age calculation, unless age is captured on the CRF.

3.7.1. Data Handling for Efficacy Endpoints

Viral load values below the limit of quantification (BLQ) reported as <LLOQ will be counted as LLOQ-1 in the summaries and order statistics. Viral load values below the limit of detection will be treated as “0”. Viral load data will be transformed using the base 10 logarithm before the analyses. In case of zero value, 1 will be added to each viral load measurement before being transformed.

The FLU-PRO score will be calculated as the sum of the scores for all symptoms collected divided by number of symptoms with non-missing score (ie, the number of symptoms collected).

3.7.2. Data Handling for Laboratory Endpoints

Laboratory data that are continuous in nature but are less than the LLOQ or above the upper limit of quantitation (ULOQ) will be imputed as follows:

- A value that is 1 unit less than the LLOQ will be used for calculation of descriptive statistics if the data is reported in the form of “< x” (where x is considered the LLOQ). For example, if the values are reported as < 50 and < 5.0, then values of 49 and 4.9 will be used for calculation of summary statistics, respectively. However, for direct bilirubin, a value of “< 0.1” will be treated as 0.09 for calculation of summary statistics.
- A value that is 1 unit above the ULOQ will be used for calculation of descriptive statistics if the data is reported in the form of “> x” (where x is considered the limit of quantitation). For example, if the values are reported as > 50 and > 5.0, then values of 51 and 5.1 will be used for calculation of summary statistics, respectively.
- The limit of quantitation will be used for calculation of descriptive statistics if the data is reported in the form of “≤ x” or “≥ x” (where x is considered as the limit of quantitation).

3.7.3. Data Handling for PK Endpoints

Natural logarithm transformation will be used for plasma concentrations and analysis of PK parameters. Plasma concentration values that are below the limit of quantitation (BLQ) will be presented as “BLQ” in the concentration data listing. Values that are BLQ will be treated as 0 at predose time points, and one-half the value of the LOQ at postbaseline time points, where LOQ is corrected for the dilution factor (ie, reported LOQ/dilution factor) for determination of summary and order statistics.

The following conventions will be used for the presentation of summary and order statistics:

- If at least 1 subject has a concentration value of BLQ for the time point, the minimum value will be displayed as “BLQ.”
- If more than 25% of the subjects have a concentration data value of BLQ for a given time point, the minimum and Q1 values will be displayed as “BLQ.”
- If more than 50% of the subjects have a concentration data value of BLQ for a given time point, the minimum, Q1, and median values will be displayed as “BLQ.”
- If more than 75% of the subjects have a concentration data value of BLQ for a given time point, the minimum, Q1, median, and Q3 values will be displayed as “BLQ.”
- If all subjects have concentration data values of BLQ for a given time point, all order statistics (minimum, Q1, median, Q3, and maximum) will be displayed as “BLQ.”

Pharmacokinetic parameters that are BLQ will be imputed as one-half LOQ before log transformation or statistical model fitting.

